6.12.6. Vital Signs and Other Physical Findings

The analysis of vital sign parameters is described in the H0P-MC-CPMP SAP Version 5.

6.12.7. Electrocardiograms

The analysis of electrocardiograms parameters is described in the H0P-MC-CPMP SAP Version 5.

6.13. Subgroup Analyses

General subgroup analyses are described in the H0P-MC-CPMP SAP Version 5.

There are no additional subgroup analyses planned.

6.14. Protocol Deviations

Participants with study important protocol deviations will be summarized by type of deviation and listed by treatment and investigative site.

Important protocol deviations for the study are described in the H0P-MC-CPMP SAP Version 5 and H0P-MC-BP01 Trial Issue Management Plans.

6.15. Interim Analyses and Data Monitoring

Interim analyses may be conducted under the auspices of an Assessment Committee according to the specifications set forth in the protocol. These analyses will be at the CPMP level and will consider data from all ongoing ISAs. Details are provided in the H0P-MC-CPMP SAP Version 5.

There are no additional interim analyses planned for H0P-MC-BP01.

6.16. Planned Exploratory Analyses

In addition, a cumulative distribution function of percent change from baseline to endpoint for the RMDQ total score will be provided for each treatment group. However, no statistical comparisons will be made between the groups.

6.17. Totality of Evidence for Safety

The totality of evidence for safety analysis has been briefly described in the H0P-MC-CPMP SAP Version 5. The key safety events to be considered for H0P-MC-BP01 are listed below by domain:

General Adverse Event Information

- Serious adverse events related to study treatment
- Study discontinuation due to adverse event
- Treatment discontinuation due to adverse event

Cardiovascular

- QTc prolongation: > 60 msec increase
- Serious cardiac disorders adverse event

Liver function

- Hy's Law case: Serum total bilirubin ≥ 2 and ALT ≥ 3 for at least one visit during the double-blind treatment period

Metabolic function

- Serious hypoglycemia adverse event
- Treatment emergent HbA1c: Shift from low/normal at baseline to high at least once during the double-blind treatment period

Renal function

- Treatment emergent abnormal eGFR: Shifts
 - Mild at baseline to moderate/severe during the double-blind treatment period
 - Moderate at baseline to severe during the double-blind treatment period

Dermatological

- Serious or severe dermal reactions

Hypersensitivity

- Moderate to severe infusion site reactions
- Serious or severe hypersensitivity reactions

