- eCOA compliance - the overall eCOA compliance analysis conducted in POC lock will be summarized for PDEP period plus at each nominal week up to Visit 801.
- Concomitant therapy – the analysis conducted in POC lock will be repeated in DB plus FU period (may also include PDEP) except the listing of rescue medication use above protocol specified limits.
- Efficacy endpoint – The weekly average pain intensity via NRS will be calculated with extension to week 12 (Visit 801). The following analysis will be conducted across all time points in DB plus FU period based on the same model conducted in DB treatment period. Nominal weeks 9-12 in the follow-up period will be derived in a similar way as described in section 6.12.1 of the H0P-MC-CPMP SAP Version 5, except that the days between V7 and V801 are split across 4 weeks.
 - Change from baseline in average pain intensity measured by weekly average of NRS
 - Change from baseline in worst pain intensity measured by weekly average of NRS
 - Change from baseline in DSA-specific physical functioning measures
 - Proportion of participants with a pain reduction from baseline greater than or equal to 30%, 50%, and 70% as measured by the average pain responses on the NRS
 - Proportion of participants with reduction from baseline greater than or equal to 30%, 50%, and 70% on DSA-specific physical function subscale
 - Overall improvement as measured by Patients' Global Impression of Change

A frequentist MMRM analysis will be conducted as a sensitivity analysis for the primary and some secondary endpoints.

A Bayesian MMRM subgroup analysis of baseline pain severity (<7, >=7) will be also evaluated for the primary endpoint. A frequentist MMRM analysis will be performed as a sensitivity analysis for subgroup analysis.

- Safety analyses for TEAEs – the following analysis will be repeated in DB plus FU period unless otherwise specified.
 - Overview of adverse event, a listing of AE (also include PDEP)
 - SAE and a listing of SAE
 - TEAE and post-treatment-emergent adverse event (PTEAE) by PT, by PT within SOC, and PT by maximum severity. A listing of TEAE and PTEAE will be provided.

- Post-treatment-emergent AE by PT, by PT within SOC for safety follow-up period only
- Adverse event of special interest (ISA specific)
- Laboratory measures – some analysis conducted in POC lock will be repeated in DB plus FU period. The additional analysis will be included but not limited to

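### In SAP 6.17 the general serious-adverse-event row counts only treatment-related events; an all-cause row by arm, deaths included, should be added

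*SAP*

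**What the plan says.** SAP 6.17 opens its list with "The key safety events to be considered for H0P-MC-BP01 are listed below by domain". The general adverse-event domain has three rows: "Serious adverse events related to study treatment", "Study discontinuation due to adverse event" and "Treatment discontinuation due to adverse event". The first is the only row in the section that takes in serious events of every kind, and it is limited by causality. No row covers SAEs regardless of cause, and none covers deaths.

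The organ-system rows have no such limit. Examples are "Serious cardiac disorders adverse event" and "Serious hypoglycemia adverse event"; the rows for serious or severe dermal and hypersensitivity events are also free of it.

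The method is not in this SAP: "The totality of evidence for safety analysis has been briefly described in the H0P-MC-CPMP SAP Version 5". Section 6.17 gives no decision rule or weighting, does not say who judges relatedness, and does not say whether counts are shown by arm.

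Elsewhere SAEs are reported without a relatedness condition. SAP 8 includes "SAE and a listing of SAE" for the double-blind and follow-up periods combined. SAP 6.19 summarises SAEs by treatment group and preferred term, with numbers at risk. SAP 6.18 provides a cumulative SAE summary and a list of deaths for periodic reports.

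**The concern.** The trial is randomised, placebo-controlled and blind to investigator and participant (protocol synopsis). Whether the antibody causes serious events can be judged by comparing event rates between arms, without deciding cause case by case. Filtering on relatedness first removes some events from that comparison.

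The general row is where this matters most. Harms that were foreseen already have their own domains. The general SAE row is the catch-all for the unforeseen ones, and a single-case judgement has least to go on there.

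At stake is the sensitivity of a pre-specified safety summary. According to the SAP revision history, 6.17 was added in Version 2, before unblinding for the proof-of-concept lock. The protocol (1.1, 2.1) says that the totality of the data will assess benefit and risk and inform development decisions.

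**Working it through.** **Which SAEs reach the list.** Reading the 6.17 rows together, an SAE is counted if at least one of these holds:

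- it is judged related to study treatment;
- it leads to discontinuation of treatment or study;
- it falls in a named domain (for example cardiac, hypoglycemia, dermal, hypersensitivity).

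The gap is an SAE that meets none of them. A serious infection judged unrelated, after which the participant continues, is an example.

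**Design figures.** The protocol synopsis gives 100 and 50 participants and 15% dropout. Expected completers are 150 × (1 − 0.15) = 127.5, which reproduces the stated 128. The point does not rest on this figure; only the arm sizes are used below.

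**Assumptions.** The documents give no SAE rates and no share judged related. I assume all-cause SAE rates of 6% (active) and 2% (placebo), with 10% and 2% as an alternative. A share q of SAEs is judged related, the same in both arms. q = 1 means that all SAEs count.

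**Formulas.**

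- Expected counts: 100 × 0.06 × q and 50 × 0.02 × q.
- Expected difference: (6 − 2) × q percentage points.
- Chance of an observed difference of at least 4 points: P(X/100 − Y/50 ≥ 0.04), with X ~ Binomial(100, 0.06q) and Y ~ Binomial(50, 0.02q), by exact enumeration. The 4-point mark is a yardstick of mine, not a rule in the plan.

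| Share judged related, q | Expected counts, 6% vs 2% | Expected difference (points) | Chance of ≥4 points, 6% vs 2% | Chance of ≥4 points, 10% vs 2% |
|---|---|---|---|---|
| 1 (all SAEs) | 6.0 vs 1.0 | 4.0 | 57% | 90% |
| 0.50 | 3.0 vs 0.5 | 2.0 | 24% | 58% |
| 0.25 | 1.5 vs 0.25 | 1.0 | 5% | 20% |
| 0.10 | 0.6 vs 0.1 | 0.4 | 0.3% | 1.7% |

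**How far this depends on an equal share.** Split the active rate into 2% background and 4% excess. Let b be the share of background events judged related (equal in both arms if judged blind) and e the share of excess events judged related. The difference is (2b + 4e) − 2b = 4e points. The background share cancels, so the shrinkage depends only on how often the excess events are recognised as related. It vanishes only if e = 1.

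**Limit of the illustration.** These figures describe the general row taken alone. SAEs that also enter through another row are still counted there. The trial is also too small to test SAE rates formally: with all SAEs counted, a one-sided Fisher test at 0.05 would be significant with probability of only 11% (6% vs 2%) or 47% (10% vs 2%). The row is for descriptive reading.

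**The case against.** The strongest defence is that a related-only row can be deliberate. It keeps unrelated hospitalisations out of a short list, and organ-system rows without the filter sit beside it. If every excess event were recognised as related and no background event were, the filter would keep the full difference and remove noise. That is coherent, so the mix of filtered and unfiltered rows is not a contradiction. But it relies on correct case-by-case recognition of unforeseen harm, and the SAP gives no reason for the choice.

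A reader might also infer more than the documents support:

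- *That an SAE excess drops out of the safety decision.* No decision rule is given here, and both the totality method and the general safety analyses are referred to the parent SAP. All-cause SAEs remain in SAP 6.18, 6.19 and 8, and the synopsis provides for a data monitoring committee.
- *That the whole list counts only related events.* Two discontinuation rows and four serious-event rows carry no such condition.
- *That the randomised comparison is thrown away.* Related SAEs can still be compared between arms. If relatedness is judged blind, the expected effect is dilution rather than bias in one direction.
- *That an investigator's opinion decides.* The assessor of relatedness is not stated.

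These points stand, and they limit the size of the concern. They do not put an unrelated-judged SAE on the key-event list. The outputs in 6.18 and 6.19 serve periodic reporting and registry disclosure, and section 8 concerns the final lock.

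**Conclusion.** The gap is narrow but real: the listed key events omit an SAE judged unrelated that causes no discontinuation and lies outside the named domains, and they have no row for deaths. The event is not lost from reporting, and the unseen parent SAP may add it to the totality assessment.

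The size scales directly with the share of excess events judged related: a true 4.0-point difference is expected to show as 2.0, 1.0 or 0.4 points at 50%, 25% or 10%. This rests on assumed SAE rates and assumed shares, with relatedness judged blind. This is an inexpensive improvement to the plan, not an error that invalidates it.

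**What to change.** In the general domain of SAP 6.17, add a row *Serious adverse events, all causality (including deaths)*, shown by arm with denominators, and keep the related events as a supporting sub-row. If the parent SAP already brings all-cause SAEs and deaths into the totality assessment, a cross-reference in 6.17 would make that visible.

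The cost is one line of the SAP. No new data are needed, because all SAEs are already summarised. The downside is that some background SAEs enter the summary; they occur in both arms, so the placebo rate gives the reference against which to read them.

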1.3. Schedule of Activities (SoA)

This SoA shows visits and procedures unique to the intervention-specific appendix (ISA) H0P-MC-BP01 (BP01) for LY3016859. Please refer to Master Protocol H0P-MC-CPMP (CPMP) and the CLBP disease-state addendum (DSA) H0P-MC-CPMP(2) SoAs for additional information.

H0P-MC-BP01 ISA										
	Randomization	Double-Blind Treatment				Follow-up			Early Discontinuation	Notes
Visit Number	V3	V4	V5	V6	V7	V801	V802	V803	ED	
Study Week	0	2	4	6	8	12	16	26		
Visit Window (days)		±3	±3	±3	±3	±5	±7	±7		Minimal interval between 2 doses cannot be shorter than 11 days.
Physical examination	X	X	X	X	X	X	X	X	X	Targeted exam for skin, eyes, mouth, lungs, and GI tract should be performed at each visit, in addition to any symptom-driven exam. Full physical exam should be performed at Visit 803 or ED.
Weight								X		
Vital signs	X	X	X	X	X	X	X	X		Includes respiratory rate, blood pressure, temperature, and pulse rate. All vital signs are collected before study intervention infusion on V3-V6.
ECG			X		X			X		Single safety ECGs
Study intervention IV infusion	X	X	X	X						1-hour IV administration The timing between randomization and the first IV infusion may be up to, but not longer than, 2 business days to reduce participant burden.
Adverse events						X	X	X		
Concomitant medication						X	X	X		
Rescue medication usage reporting						X				If the participant discontinues after V801, this assessment is not needed for ED per the CPMP SoA.
NRS						X				If the participant discontinues after V801, this assessment is not needed for ED per the CPMP SoA.
PGI						X				If the participant discontinues after V801, this assessment is not needed for ED per the CPMP SoA.

H0P-MC-BP01 ISA										
	Randomization	Double-Blind Treatment				Follow-up			Early Discontinuation	Notes
Visit Number	V3	V4	V5	V6	V7	V801	V802	V803	ED	
Study Week	0	2	4	6	8	12	16	26		
Visit Window (days)		±3	±3	±3	±3	±5	±7	±7		Minimal interval between 2 doses cannot be shorter than 11 days.
RMDQ						X				If the participant discontinues after V801, this assessment is not needed for ED per the CPMP SoA.
C-SSRS						X		X		Use C-SSRS Since Last Visit version.
Self-Harm Supplement Form						X		X		
Self-Harm Follow-up Form						X		X		Required if triggered by the Self-Harm Supplement Form per instructions.
Hematology						X	X	X		
Chemistry		X		X		X	X	X		
Urine Chemistries	X	X	X	X	X	X		X	X	
Urinalysis								X		

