4.4. End of Study Definition

A participant is considered to have completed this ISA if he or she has completed all required phases of the study including the last scheduled procedure shown in the ISA SoA.

The end of the study is defined as the date of the last visit of the last participant in the study or last scheduled procedure shown in the ISA SoA for the last participant.

5. Study Population

The CPMP Master Protocol and CLBP CPMP(2) DSA provide eligibility criteria that must be followed for this study. LY3016859-specific inclusion and exclusion criteria are listed here.

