8.1.2. Electrocardiograms

Single 12-lead ECG will be obtained as outlined in the SoA using an ECG machine that automatically calculates the heart rate and measures pulse rate, QRS, QT, and corrected QT interval (QTc).

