 - Summary of laboratory measures with box plot for observed value and change from baseline by visit, and shifts to high/low.
 - The shift table of eGFR at baseline vs. postbaseline by minimum, maximum and last observed eGFR result will be summarized.
 - Summary of hepatic function laboratory maximum observed result at baseline and any postbaseline will be presented.
- Vital signs – some analysis conducted in POC lock will be repeated for combined DB plus FU period.
- ECG - some analysis conducted in POC lock will be repeated for combined DB plus FU period. Additionally, a summary of ECG measures and boxplot will be provided as well as a listing of out of range of ECGs.
- Protocol deviations - summary of important protocol deviation will be conducted in DB plus FU period.

9. References

10. Appendices

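### SAP 6.17 judges QTc prolongation by change alone, so a very long absolute QTc reached after a rise of 60 msec or less is not a cardiovascular key safety event unless a serious cardiac adverse event is recorded.

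*SAP*

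**What the plan says.** SAP 6.17 introduces its list with "The key safety events to be considered for H0P-MC-BP01 are listed below by domain". The cardiovascular domain has two rows: "QTc prolongation: > 60 msec increase" and "Serious cardiac disorders adverse event". The QTc row names no absolute value, correction formula, baseline definition or observation window.

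Other measured parameters in the list are judged by the level or category reached. The Hy's Law row uses bilirubin and ALT thresholds, the HbA1c row a shift to high, and the eGFR row a shift to a worse category. The same list has rows for stopping treatment, and for leaving the study, because of an adverse event.

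ECG data appear in four other places:

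- Protocol 1.3 schedules ECGs at Visits 5, 7 and 803, noted as "Single safety ECGs". Protocol 8.1.2 says the machine measures QTc. A baseline ECG would have to come from the master protocol schedule.
- SAP 6.12.7 defers the general analysis: "The analysis of electrocardiograms parameters is described in the H0P-MC-CPMP SAP Version 5".
- SAP section 8 adds at final lock: "a summary of ECG measures and boxplot will be provided as well as a listing of out of range of ECGs". The range limits are not given.
- The opening of Protocol section 5 says: "The CPMP Master Protocol and CLBP CPMP(2) DSA provide eligibility criteria that must be followed for this study". The appendix's own criteria (5.1 and 5.2) set no QTc limit.

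**The concern.** A change criterion and an absolute criterion find different people. Someone whose QTc is already towards the long end at baseline can reach a very long value without rising more than 60 msec. Without an absolute limb, the row is blind to that person. The serious-adverse-event row does not help, because an ECG value on a scheduled visit, with no symptoms, is not in itself a serious adverse event.

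What is at stake is one row of one safety summary. SAP 6.17 is where this trial's key safety events are gathered by domain, so a reader of its cardiovascular domain would not see such a case there. The primary analysis and the sample size do not depend on it.

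**Working it through.** The plan gives no figure to reproduce on this point, so the check applies the rule as written and then sizes the gap under stated assumptions.

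**1. The rule applied.** A participant is counted if post-baseline QTc − baseline QTc > 60 msec.

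| Baseline | Post-baseline | Change | Counted? |
|---|---|---|---|
| 455 | 512 | +57 | no |
| 445 | 505 | +60 | no |
| 460 | 515 | +55 | no |
| 480 | 520 | +40 | no |

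All four end above 500 msec, the absolute limit assumed here.

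**2. Who can be missed.** For an absolute limit T, a participant who only just passes T is missed if baseline is T − 60 or higher. For T = 500 that is 440 msec or higher; for T = 480 (also assumed) it is 420 msec or higher. A long-baseline participant who rises by more than 60 msec is counted.

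**3. Size. Every input is an assumption.** Baseline QTc is normal with mean 415 and SD 22 msec. There are two on-treatment ECGs (Visits 5 and 7), and their changes from baseline are drawn independently with mean d and SD s of 12 to 20 msec. The limit is 500 msec. C is the larger of the two changes. A participant is missed when baseline + C > 500 and C ≤ 60. Two million participants were simulated per scenario, and the ranges below run over s.

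| Mean rise d | Exceed 500, per 100 | Missed by the row, per 100 | Missed per 100 if baseline is capped at 450 |
|---|---|---|---|
| 0 | 0.06–0.4 | 0.06–0.35 | 0–0.02 |
| 20 | 0.8–2.6 | 0.8–1.6 | 0.02–0.24 |
| 40 | 5.7–11 | 3–4 | about 0.8 |

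The LY3016859 arm has 100 participants, so the entries are also expected counts for that arm.

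**4. What the existing row would already show.** The chance that at least one of the two changes exceeds 60 is 1 − Φ((60 − d)/s)².

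- For d = 40: 1 − Φ(1.67)² = 0.093 at s = 12, and 1 − Φ(1)² = 0.292 at s = 20, so 9 to 29 per 100.
- For d = 20: 1 − Φ(3.33)² = 0.001 at s = 12, and 1 − Φ(2)² = 0.045 at s = 20, so 0.1 to 4.5 per 100.

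With a large drug effect the row is far from empty. The gap matters most, relative to what is counted, when the mean rise is moderate, the variation is small and baseline is not capped.

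**The case against.** The strongest reply is that the visible text is not the whole plan. SAP 6.17 says the parent SAP also describes this analysis briefly, and SAP 6.12.7 sends the ECG analysis there; absolute QTc categories may already exist in it. Master protocol eligibility may exclude a long baseline QTc, which would remove most of the missed cases. The final-lock listing could show a value of 512 msec, and a participant who stopped because of it would enter a discontinuation row. The documents show no QT concern for this antibody: the risk table in Protocol 2.3.1 lists none. SAP 6.17 also states no decision rule or weighting for its events.

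All of this stands, and it limits the weight of the point. It does not change what the QTc row counts. The listing has no stated limits and is not part of the key-event summary, and the discontinuation rows apply only if the finding led to stopping.

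A reader might go further in two ways that the documents do not support:

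- One is that long QTc values would go unreported, or that the cardiovascular domain would look clean despite a real effect. The listing and the unseen parent SAP leave the first open. Step 4 of the working contradicts the second for a large effect.
- The other is that the row is wrong to count a rise of more than 60 msec that ends in the normal range, such as 370 to 432 msec (+62). A large change can be a signal in itself, and detecting it is the purpose of a change criterion.

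**Conclusion.** The point holds in a limited form. As written, the cardiovascular key events in SAP 6.17 omit a participant whose QTc becomes very long after a rise of 60 msec or less, unless a serious cardiac adverse event is also recorded. The rule establishes this without any assumption.

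The size does depend on assumptions: the baseline distribution, the spread of change, the mean rise and the 500 msec limit. On those inputs the expected number missed in the LY3016859 arm is well below one with no drug effect, about one or two at a mean rise of 20 msec, and three or four at 40 msec. Under an assumed baseline cap of 450 msec it is below one in every scenario. Whether such a cap exists cannot be checked without the master protocol and the disease-state addendum.

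This is a low-priority but inexpensive improvement to one safety definition.

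**What to change.** First check whether the CPMP SAP Version 5 defines an absolute QTc category. If it does, use that category in the SAP 6.17 row. If it does not, extend the row to read: a QTc increase of more than 60 msec from baseline, or a post-baseline QTc above an absolute limit (for example 500 msec) not present at baseline. Report the change limb and the absolute limb separately and together, by treatment arm.

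The cost is one line in the SAP and one additional flag on ECGs already scheduled, with no new data collection. The downside is a rare extra event in either arm: with no drug effect, about 0.06–0.35 per 100 on the inputs above.

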Appendix 1. Planned Laboratory Analytes and Direction of Interest

The H0P-MC-CPMP SAP Version 5 describes tests that may be performed broadly for the Chronic Pain Master Protocol. This table describes additional tests in H0P-MC-CPMP.

Chemistry	CCI	Other Tests
Cystatin-C		Immunogenicity
		Serum Epiregulin
		LY3016859 concentration
		Urine pregnancy

Leo Document ID = 10f50551-87b2-4a58-a289-175366533963

Approver: PPD

Approval Date & Time: 06-Dec-2021 21:18:26 GMT

Signature meaning: Approved

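### The Hy's Law event in SAP 6.17 has no unit, no multiple of the upper limit of normal and no AST: read literally in U/L its ALT limb tests nothing, and read as × ULN it does not count an AST-led case

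*SAP*

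**What the plan says.** SAP 6.17 (Totality of Evidence for Safety) opens with "The totality of evidence for safety analysis has been briefly described in the H0P-MC-CPMP SAP Version 5" and continues "The key safety events to be considered for H0P-MC-BP01 are listed below by domain". The analysis is therefore sketched in the master SAP, but the event list for this study is set in 6.17. Under liver function the list has one entry: "Hy's Law case: Serum total bilirubin ≥ 2 and ALT ≥ 3 for at least one visit during the double-blind treatment period".

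The cardiovascular entry in the same list does carry its unit: "QTc prolongation: > 60 msec increase". According to the SAP's revision history, 6.17 was added in Version 2, and Version 3 records no change to it.

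The only other hepatic analysis visible in the SAP is in Section 8: "Summary of hepatic function laboratory maximum observed result at baseline and any postbaseline will be presented". It names no analyte and no threshold. For the general laboratory tests, Appendix 1 points elsewhere: "The H0P-MC-CPMP SAP Version 5 describes tests that may be performed broadly for the Chronic Pain Master Protocol". AST does not appear in the supplied text of either document.

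**The concern.** A cut-off of 2 for bilirubin and 3 for ALT means different things in mg/dL, µmol/L, U/L or multiples of ULN, and the line does not say which applies. Two programmers working from this text could produce different counts for the same data. The choice of aminotransferase is a separate matter: with ALT alone, liver injury that shows mainly in AST is outside the definition.

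The protocol synopsis says that the totality of the data will be used to weigh benefit against risk and to inform further development. With about 100 participants on LY3016859 and 50 on placebo, a single flagged or uncounted case could change what the liver entry shows.

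**Working it through.** The plan states no figure here that could be reproduced. This is a check of a definition, carried through on example values.

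**Inputs.** From SAP 6.17: bilirubin cut-off 2, and for the enzyme limb "ALT ≥ 3 for at least one visit". Assumed, because the documents give no reference limits: ALT and AST ULN 30 to 55 U/L (ALT 0.5 to 0.92 in µkat/L); bilirubin ULN 1.0 to 1.5 mg/dL, or 17 to 26 µmol/L.

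**Step 1: the literal cut-offs as a fraction of ULN (cut-off ÷ ULN).**
- ALT in U/L: 3/30 = 0.10; 3/40 = 0.075; 3/55 = 0.055. A normal ALT meets the limb.
- ALT in µkat/L: 3/0.5 = 6.0; 3/0.92 = 3.26. A normal ALT does not meet it.
- Bilirubin in mg/dL: 2/1.0 = 2.0; 2/1.5 = 1.33.
- Bilirubin in µmol/L: 2/17 = 0.118; 2/26 = 0.077. A normal bilirubin meets the limb.

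**Step 2: the same cut-offs as multiples of ULN.**
- ALT: 3 × 30 = 90 to 3 × 55 = 165 U/L.
- Bilirubin: 2 × 1.0 = 2.0 to 2 × 1.5 = 3.0 mg/dL, or 2 × 17 = 34 to 2 × 26 = 52 µmol/L.

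**Step 3: three rules on example participants.** The assumed ULNs are 40 U/L for both enzymes and 1.2 mg/dL for bilirubin, so the × ULN cut-offs are 120 U/L and 2.4 mg/dL.

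| Bilirubin (mg/dL) | ALT (U/L) | AST (U/L) | Literal, U/L and mg/dL | × ULN, ALT only | × ULN, ALT or AST |
|---|---|---|---|---|---|
| 2.1 | 20 | 20 | flagged | no (2.1 < 2.4) | no |
| 3.0 | 100 | 200 | flagged | no (100 < 120) | flagged (200 ≥ 120) |
| 3.0 | 160 | 100 | flagged | flagged | flagged |

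Row 1 shows the fault of the literal reading: with a normal ALT, bilirubin alone produces the flag. Row 2 shows the fault of the × ULN reading: the AST-led case is not counted. It also shows that the literal rule does catch that case, because its ALT is far above 3 U/L. Row 3 is counted under every rule.

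**The case against.** The best defence is that a line labelled as Hy's Law will be understood as multiples of ULN by anyone who programs it, so only notation is missing. That is probably the intent, and it makes literal coding unlikely in practice. Other entries in the list are also shorthand: the eGFR severity grades and the high HbA1c category have no cut-offs either, which suggests a summary resting on definitions held elsewhere. Those definitions could be in the master SAP Version 5 or in SAP 6.12.4 (Clinical Laboratory Evaluation), which is in the table of contents but whose text is not available. This cannot be excluded. It still leaves 6.17 without the multiple and without a pointer to it.

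On AST, nothing in the supplied documents says it belongs in the definition. That stands, so the AST part of this point describes which cases the rule counts; it does not show a departure from a stated standard.

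On impact, a clinically important hepatic event could also enter through the entries for treatment-related serious adverse events or for discontinuation of treatment or study due to an adverse event. The Section 8 summary of maximum hepatic results is a partial safeguard. No visible decision rule gives a single case a fixed weight.

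**Conclusion.** The event is under-specified as printed, and each of the two main readings has its own fault. Literally in U/L, the ALT limb excludes almost no one. As × ULN, a case with AST at or above 3 × ULN and ALT below it is left out.

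Three stronger conclusions might be inferred, and the documents do not support them:
- That the rule both over-flags normal ALT and misses AST-led cases. The first needs the literal reading and the second needs the × ULN reading, so they cannot both hold.
- That a normal ALT by itself creates a case. Bilirubin must still reach 2.
- That most participants, or some predictable number, would be falsely flagged. Flagging nearly everyone needs ALT in U/L and bilirubin in µmol/L, both coded literally. A count in mg/dL needs a prevalence of isolated raised bilirubin, which the documents do not give.

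The size is therefore small. The documents give no hepatic event rate; I assume true events are near zero in about 150 participants, and the protocol's exclusion of serious or unstable hepatic disease (criterion 2004) is consistent with that. The conclusion rests on the assumed reference limits and on no definition being supplied in the master SAP or in SAP 6.12.4. It is worth correcting because the printed threshold is incomplete and the repair is cheap.

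**What to change.** In SAP 6.17, replace the liver entry with: *Potential Hy's Law case: total bilirubin ≥ 2 × ULN and (ALT ≥ 3 × ULN or AST ≥ 3 × ULN)*, keeping the existing time window. Align it with any definition in the master SAP Version 5 and cite that section if there is one. Add a listing of each flagged participant for case review.

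This changes analysis text only. The cost is one line of the SAP, one line of code and a short listing. It assumes AST is in the master-protocol chemistry panel, which the supplied documents do not show. The one downside is an occasional flag from an AST rise of muscle origin, which the listing review would resolve.
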